15.2 Study Schedule

	Visit 1 Screening		Visit 2 Baseline visit		Visit 3 Telephone	Visit 4	Visit 5	Visit 6	Visit 7	Visit 8 Telephone
Time	-14 days +/- 2 days	0	0a	0b	Week 8 +/- 5 days	Week 26 +/- 7 days	Week 52 +/- 7 days	Week 76 +/- 7 days	Week 104 +/- 7 days	Week 106 +/- 2 days
Confirm UK Queen Square Brain Bank Criteria met	X									
Review onset of cognitive symptoms $(\leq 1$ year onset from motor symptom is an exclusion)	x									
Capacity Assessment	Х						Х			
Informed consent	Х									
Beck Depression Inventory	X									
ACE-R ¹	Х									
ECG	Х									
Medical History	Х									
Haematology & biochemistry ²	X						X		X	
Mattis DRS-2 ³	Х		Х			Х	Х	Х	Х	
10-item NPI ⁴			X			Х	Х	Х	Х	
BADLS ⁵			Х			Х	Х	Х	Х	
Quality of life questionnaires ⁶			X			Х	X	Х	Х	
CSRI ⁷			X			Х	Х	Х	Х	
UPDRS ⁸	X		X			X	X	Х	Х	

Page | **36**

Modified ADCS-CGIC ⁹		X			Х	Х	Х	Х	
MoCA		X			Х	Х	Х	Х	
PD-CRS		Х			Х	Х	Х	Х	
SCOPA-cog		Х			Х	Х	Х	Х	
ABC		Х			Х	Х	Х	Х	
Provision of falls diary		Х			Х	Х	Х		
Randomisation (after all eligibility checked)			Х						
Study medication dispensed ¹⁰			Х		X	Х	Х		
Study medication checked					Х	Х	Х	Х	
Adverse events				Х	Х	Х	Х	Х	Х
Concomitant medications	Х	X		Х	Х	Х	Х	Х	

MUSTARDD-PD Protocol Version 7.0, 22 August 2013

 Addenbrooke's Cognitive Examination; 2: full blood count, vitamin B12 and biochemical (urea and electrolytes, random blood glucose, thyroid function tests and liver function tests); 3 Mattis Dementia Rating Scale; 4: 10-item Neuropsychiatric Inventory; 5: Bristol Activities of Daily Living Scale;
 comprise EQ5D, DEMQOL, DEMQOL-proxy, and Scale of Quality of Life of Caregivers; 7: Client Service Receipt Inventory;
 Motor Subsection of the 2008 Movement Disorder Society-sponsored Unified Parkinson's Disease Rating Scale, 9: Baseline CGIC interview only, visits 4, 5, 6 & 8 interview & scoring 10: Patient commences medication

15.3 Data Handling and Record Keeping

Data collection and transfer in this study will comply with NRES and Caldicott guidelines and the Data Protection Act (1998). The quality and retention of study data will be the responsibility of [name], as Chief Investigator. All study data will be retained in accordance with the latest Directive on GCP (2005/28/EC) and local policy.

All patients will be allocated a unique study identifier, which will be used on all data collection forms and questionnaires to preserve confidentiality; names and addresses will not appear on completed questionnaires or case report forms. Only a limited number of members of the research team will be able to link this identifier to patient-identifiable details (name, date of birth (DOB) and address).

All study documentation will be held in secure offices, which will not be open to the public. All members of the research team with access to identifiable or anonymised data will operate to a signed code of confidentiality. Transmission of hard-copy records (e.g. CRFs, questionnaires) between sites and the NCTU will be by secure fax, post or hand delivery by the research nurses / Trial Manager. Participants will be informed in the patient information sheet about the transfer of information to the NCTU and about levels of access to patient identifiable data, and will be asked to consent to this. Any data used in publications from MUSTARDD-PD will be fully anonymised; it will not be possible to identify individual patients from such publications.

Study data will be entered from source, paper CRFs and questionnaires into a 21 CFR part 11 compatible clinical data management software package for processing and management, allowing a full audit trail of any alterations made to the data post entry. Access to the NCTU study databases will be password protected. All personal information obtained for the study will be held securely at the trial sites and will be treated as strictly confidential. Site numbers, screening and randomisation codes will permit the removal of much personal detail (eg name and address) prior to transfer of data to the trial office in Newcastle.

Long term data storage

At the end of the study, original questionnaires, case report forms and consent forms will be securely archived for 15 years following publication of the last paper or report from the study, in line with Sponsor policy and NCTU standard operating procedures. This will also allow any queries or concerns about the data, conduct or conclusions of the study to be resolved.

Data sharing

Permission for data sharing with third parties at the end of the study will be sought from all participants, the appropriate Research Ethics Committees and Caldicott Guardians. All data to be shared will be anonymised, with a unique study identifier (for patient or carer as appropriate) allowing linkages between multiple records and files. The quantitative data sets will be fully documented both in terms of internal labelling (eg in 'system' files for commonly used statistical packages such as SPSS and STATA) and external description (data dictionary). These data sets will be prepared during the last 4 months of the study. For the first 24 months after the end of the study, the data will only be available to members of the study team (while papers are being prepared for publication). Thereafter, the quantitative data sets will be made available for independent, external usage. Formal application and registration to use the data will be required.

All efforts should be made to collect all study date for each visit. If a patient is unable to attend a study visits, even with the + 7 days window, due to ill health the following two items should be conducted over the telephone with the care-giver/informant:

BADL NPI-10

16. Statistical Considerations

The primary outcomes, the DRS, NPI-10 and the BADLS, will be assessed at baseline and then at weeks 26, 52, 76 and 104.

16.1 Statistical Analysis

Analysis will be on the basis of intention to treat. The main statistical challenge in analysing such data is to take into account incomplete data which will be due to a number of factors including the occurrence of side effects or the death of individual participants. Although approximately 50% of patients are expected to discontinue medication prematurely during the study, the actual loss to follow up at 104 weeks is expected to be around 20%, yielding 80% of the original group providing data on the primary outcome measures at 104 weeks. It is likely that those participants who are lost to follow up during the trial may also be people with a tendency to experience poorer outcomes (in terms of the DRS scores) than those who remain in the study.

It is necessary to take into account any difference in dropout rates and the non-randomness of the drop out when comparing functional status between the two treatment groups. This will be done by jointly modelling "survival in the study" and the repeated measures of functional status simultaneously ³³ using software that has been developed as part of an MRC funded programme of work (Grant G0400615; Statistical methodology for longitudinal studies in clinical research; Williamson PR, Diggle PJ and Henderson R). Time to drop-out will be analysed using a Cox proportion hazards model incorporating random effects. Functional outcomes will be modelled using mixed models appropriate for repeated measures. A key feature of each of these models is that within each it is possible to fit a latent variable that can be conceptualised as the patient's propensity to experience poor outcomes (both their likelihood to drop out of the study and their likelihood to have poor DRS scores). It is the inclusion of this latent variable that allows us to adjust our estimates of the treatment effect to allow for the different rates of drop out in each group. Both models are estimated simultaneously; parameter estimates are based on maximising the joint likelihood over both the survival and repeated measures data.

Within this framework we will estimate the effect of donepezil hydrochloride on our primary outcomes allowing for key baseline covariates including disease severity and possible differences between centres. The NPI-10 and BADLS scores will be analysed using the same method because there may be differential drop-out in the two treatment groups and, in addition, we cannot assume that the propensity of the subject to drop out of the study will not be correlated with the propensity of the carer to experience poor outcomes. Secondary outcomes in the form of repeated measures will be analysed using the same procedures.

No interim analysis is planned unless specifically requested by the Trial Steering Committee.

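### The joint model's drop-out event is leaving the study, so it does not cover a DRS-2 that stops while telephone follow-up continues

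*Protocol*

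**What the plan says.** Section 16.1 of the protocol holds that unequal and non-random drop-out must be allowed for, and gives that job to a joint model of remaining in the study and the repeated scores. On the event side: "Time to drop-out will be analysed using a Cox proportion hazards model incorporating random effects". A latent variable shared by the two parts represents the participant's tendency to do badly, "both their likelihood to drop out of the study and their likelihood to have poor DRS scores". The correction rests on it: "It is the inclusion of this latent variable that allows us to adjust our estimates of the treatment effect".

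The NPI-10 and BADLS receive the same method, again with reference to "the propensity of the subject to drop out of the study". Repeated secondary outcomes follow the same procedures. No outcome is given an event of its own. The section also takes a 20% loss to follow-up to mean that 80% supply the primary outcomes at 104 weeks.

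Section 15.3 adds a fallback for visits missed through illness: "the following two items should be conducted over the telephone with the care-giver/informant". Those items are the BADLS and the NPI-10; the DRS-2 is not among them. The condition for using this route is worded as "If a patient is unable to attend a study visits, even with the + 7 days window, due to ill health".

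**The concern.** For the DRS-2, leaving the study and ceasing to provide the score are different events. A participant followed only by telephone has not dropped out, yet may never give another DRS-2. The absence is health-related by the protocol's own description, and 16.1 expects participants who are lost to have poorer DRS scores. The model nevertheless records this participant as a survivor, which pulls the latent variable towards a good course, and it contains no term for the missing DRS-2.

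At stake is the 104-week contrast on one of three primary outcomes. EQ-5D, DEMQOL, DEMQOL-proxy and the carer scale are also absent from the telephone list and are analysed by the same procedures, so they share the difficulty. The NPI-10 and BADLS are collected by telephone and do not.

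**Working it through.** **1. The plan's own figure.** Section 16.2 gives SD 13.5, difference 4.4, two-sided 5%, and 200 per arm after 20% loss from 250. The standard error is 13.5 × √(2/200) = 1.35. Power is Φ(4.4/1.35 − 1.96) = Φ(1.30) = 0.903. For the NPI-10, 3.9/(12.0 × √(2/200)) = 3.25 and power is 0.901. The stated 90% reproduces.

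**2. What the likelihood does.** Write participant i's contribution as

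L = ∫ f(observed DRS-2 | b) × h(T | b)^d × S(T | b) × φ(b) db,

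with b the latent variable, T the event or censoring time and d the event indicator. Take a participant who moves to telephone-only follow-up after the week-26 DRS-2 and stays to week 104.

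| Event used | d | T |
|---|---|---|
| Leaving the study | 0 | week 104 |
| No further DRS-2 | 1 | week 52 |

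In the first row nothing in L depends on why the later DRS-2 is absent. It is ignorable given the observed data, and S(104 | b) favours values of b that mean a good course.

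**3. Does it matter in a fitted joint model?** All parameters here are assumptions, because the protocol gives none. DRS-2 at weeks 0, 26, 52, 76 and 104; random intercept SD 9, random slope SD 2.2 per 26 weeks, residual SD 5. True placebo slope −2.00 per 26 weeks and true 104-week difference 2.00. Hazards of exit and of becoming telephone-only both rise with a worse slope, and telephone-only status is permanent. One data set of 12,000 per scenario, 18.7% leaving the study, with a discrete-time hazard at visits standing in for the Cox model.

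| Telephone-only at week 104 (placebo / donepezil) | No drop-out model | Event: leaving study | Event: last DRS-2 |
|---|---|---|---|
| 0 / 0 | 1.89 | 1.87 | 1.87 |
| 12.1% / 12.8% | 1.97 | 1.94 | 1.90 |
| 18.1% / 8.5% | 1.21 | 1.20 | 1.82 |
| 7.9% / 19.0% | 2.71 | 2.68 | 2.00 |

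For complete data the sampling error of one such difference is about 4 × √(2.2² + 25/10) × √(2/6000) = 0.20. The informative comparison is therefore along a row, on the same data. With unequal rates the study-exit event performs like no drop-out model, and the DRS-2-specific event removes most or all of the bias. With near-equal rates the difference barely moves, although the placebo slope is −1.74 with the study-exit event and −1.98 with the other.

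**4. Trial-sized check and the role of return.** Assumptions: 250 per arm, true effect 3 points, intercept variance 90, slope variance 25 (SD 5 points per year), residual SD 5, 20% non-informative exits, telephone-only gaps dependent on the participant's own slope and treated as ignorable. This uses generalised least squares, not a joint model. Ranges cover two independent runs where available.

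| Telephone rate (placebo / donepezil) | Bias, gap permanent | Bias, one visit missed |
|---|---|---|
| 10% / 10% | 0.00 to 0.03 | not run |
| 12% / 6% | −0.30 to −0.45 | −0.04 to −0.05 |
| 15% / 5% | −0.52 to −0.81 | −0.03 to −0.07 |

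The largest value is 0.81/4.4 = 18% of the design difference and 0.81/1.35 = 0.6 of the design standard error.

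**5. Power, as a side effect.** If a further share t has no week-104 DRS-2, n per arm is 250 × (0.8 − t). For t = 5%, 10%, 15% and 20% this is 187.5, 175, 162.5 and 150, and power for 4.4 points is 88.4%, 86.2%, 83.6% and 80.6%. These shares are also assumed.

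**The case against.** The strongest reply is that 15.3 describes what to do at a visit, not a permanent state. Someone ill at week 52 may return at week 76 and give a DRS-2. That stands: the bias is then close to zero and a DRS-2-specific event changes nothing. The concern is confined to participants whose DRS-2 does not resume.

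It can also be said that 16.1 never formally defines drop-out, that equating retention with supplying the primary outcomes could be read as outcome availability, and that event dates belong in a statistical analysis plan. An unseen plan may indeed define the event per outcome. But 16.1 repeatedly describes the event as dropping out of the study, and a plan that followed it literally would inherit the mismatch.

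The sizes depend on assumed imbalances between arms of roughly 2:1 to 3:1, permanent loss, and dependence on the participant's own slope. Ill health may be an intercurrent illness unrelated to cognition. That stands too.

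A reader might infer that the plan loses its sickest participants, or that the result will be biased against donepezil. The documents support neither. They say only that ill health prevented attendance, and the reverse imbalance gives 2.68 against a true 2.00, in donepezil's favour.

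**Conclusion.** The point holds in limited form. As written, the event in 16.1 does not match the way the DRS-2 can be lost under 15.3, so a permanent loss by the telephone route falls outside the adjustment. This is a stated rule that fits the DRS-2 poorly, not merely a detail left open.

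Bias in the treatment difference needs two further conditions: the loss is permanent, and it differs by arm. Section 16.1 itself allows that drop-out may differ between groups, but the protocol gives no telephone-only rate. With the assumed imbalances the bias was about 0.3 to 0.8 points in the trial-sized check, and about 0.7 to 0.8 on a true difference of 2.00 in the joint model, with its sign set by which arm loses more. With similar rates it was negligible. It is worth correcting before unblinding because the correction is cheap. The documents do not show that the result would be materially biased.

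**What to change.** In section 16.1, and in the statistical analysis plan, define the drop-out event separately for each outcome. For the DRS-2:

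- A participant with no week-104 DRS-2 has the event at the first scheduled visit from which no further DRS-2 is obtained, whether or not telephone follow-up continues. If only the baseline score exists, that is week 26, so no event falls at time zero.
- A participant with a week-104 DRS-2 is censored at week 104. Without this rule, completers could be counted as events.
- A missed DRS-2 followed by a later one is an intermittent gap, not an event.

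Apply the same rule to the secondary outcomes not collected by telephone. For the NPI-10 and BADLS, telephone scores count as observed. Report telephone-only visits by arm and visit, so that readers can see whether the imbalance that matters occurred.

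The cost is a short definition and one table. It needs no new data, no different model class and no change to visits. Event times will fall on the four follow-up visits, so the handling of ties should be stated.

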16.2 Sample Size Calculation

Although not rigorously defined, a difference of 5-6 points in DRS-2 has previously been considered to be "clinically significant" ³⁴ and 2 points on the NPI-10 as "significant" ¹². We believe the latter is likely to be of dubious *clinical* significance to the patient and carer, however, and have thus adopted a difference of 3-4 points for the sample size calculation. From previous longer term dementia trials in AD, we anticipate that 50% of the study participants may discontinue medication during the trial. We hope however to retain 80% (i.e. lose only 20%), by encouraging those subjects who withdraw prematurely from medication to adhere to the follow-up schedule for ongoing assessments.

Assuming a loss to follow-up rate at 24 months of 20% we will recruit a total of 500 patients (two groups of 250) to the trial in order to ensure complete data on 400 patients (two groups of 200). This final sample size will give us 90% power to detect a difference between groups of 4.4 in the mean DRS score and 3.9 in mean NPI-10 score. The calculation assumes a two tailed hypothesis test, a type 1 error rate of 5% and that the standard deviations of the DRS and NPI-10 scores are 13.5 and 12.0 respectively, yielding effect sizes of 0.325 in each case.

An effect size of 0.325 on the BADLS will correspond to a difference in mean scores of around 3.2. Although the range of scores possible is 0-60, the spread of values found is usually narrower than this. The BADLS has good sensitivity and specificity in differentiating change in dementia, with cut-off for improvement having previously been determined to be < -3 points, and for decline of > 1. The sample size will therefore provide us with adequate power to detect clinically significant differences in these primary outcome measures.

16.3 Health Economics Analysis

Data on health and social service utilisation patterns, medication, and (unpaid) carer inputs will be collected and calculated for each participant, based on data collected using a modified version of the CSRI. This instrument has been tailored recently for use in a number of studies of older people with dementia, and will be adjusted as needed for this study. Questions will ask about care and support over the period since previous interview. Unit costs will be attached using national figures taken from the Quality-Adjusted Life Year (PSSRU) annual compendium, where available, and from individual service providers as necessary (particularly for individual hospitals and care homes, given the inherent unit cost variation between settings).

Costs will be combined with each of the primary measures in turn and with Quality-Adjusted Life Year (QALY) gains, allowing for a parallel series of cost-effectiveness analyses. We will analyse changes in cognitive function in Parkinson's disease for patients administered donepezil hydrochloride and placebo over 104 weeks using the DRS-2, and then calculate the difference in effectiveness. We will measure costs over the same period, covering all health and social care services used, medication and unpaid carer time. An incremental cost-effectiveness ratio will be computed, and a cost-effectiveness acceptability curve will be plotted, generated from the net benefit approach and using bootstrap regression for a range of values of willingness to pay for incremental improvements in cognitive function on the DRS-2. The difference in, first, Behavioural and Psychological Symptoms of Dementia (BPSD) for patients allocated to both groups over the study period using the NPI will then be assessed,

and then the difference in activities of daily living using the BADLS will be assessed. Again, incremental cost-effectiveness ratios and acceptability curves will be used as needed.

A secondary economic evaluation will examine QALY gains for people with dementia. The QALY gains will be computed based on both the EQ5D and DEMQOL. Again, an incremental cost-effectiveness ratio and acceptability curve will be used as needed. The incremental values for QALY gains for these analyses can be guided by, for example, the implicit NICE threshold.

Each cost-effectiveness analysis will be conducted from the perspective of (a) the NHS and social services, and (b) society as a whole. The main difference will be the exclusion of the costs of unpaid care and any out-of-pocket payments by carers. Payments by patients/users or families for services will need to be measured; whether or not they are treated as health and social care system costs is dependent on a number of things, including future policy as to the funding of long-term care. The study will assess the sensitivity of findings to different assumptions regarding key assumptions made in the analyses.

16.4 Cognitive Scales Performance Analysis

Prior to study completion of the last enrolled patient, all analyses comparing cognitive assessment instruments will be based on blinded study data (*i.e.* donepezil- and placebotreated patients combined). These interim analyses comparing the different neurocognitive instruments will use the CGIC score as the primary outcome measure for clinical improvement. Once the last enrolled participant has completed the study, additional analyses will examine ability of the various neurocognitive instruments to specifically detect cholinesterase inhibitor treatment effects (*i.e.* donepezil hydrochloride versus placebo assignment) on cognition.

Analysis of the outcome variables can best be understood as slopes of scale score change over the length of the study. These slopes may be affected by many covariates, including treatment assignment, initial score on the outcome variables, some demographic/disease features and perhaps site of enrolment. The basic analytic approach will utilize a mixed model in which changes in the outcome measures over time will include a fixed effect of treatment group assignment and random effects of intercepts (the scale scores at baseline) that will be included to have both random variation (person-specific) and specific variation associated with rate of change in outcome. Adjustments for possible confounding covariates (demographics; site, etc) will be included.

Data exploration, graphical representations and analysis of residuals will be used to assess the potential impact of problems such as correlations of the various scale scores within a given subject, and to potentially inform decisions of appropriate transformations, if required. To assess the "best" scale for assessing change in cognition, both linear modelling of each scale's effect size (determined from the mixed model analysis of change over time by treatment), and analysis of sensitivity/specificity of different cut-off scores by receiver-operator characteristic analyses (ROC) will be employed.

17. Compliance and Withdrawal

